8.3.3 Visit 4-6: Follow Up Visits (Week 4, 12, 24) Post-Injection

Follow up visits will occur within 30 ± 7 days of final injection (V3). Refer to table 1 for procedures to be performed at the follow up visits visit.

9. Investigational Product

9.1 Preparation of IP

Autologous Platelet-Rich Plasma (PRP) is prepared by taking 120 mL aliquots of anticoagulated blood (120 mL whole blood and 16 ml anticoagulant citrate dextrose formula A) obtained from each treatment subject by venipuncture. Each aliquot is processed by an autologous platelet separator (Arthrex Angel, Arthrex Inc., Naples, Florida) to yield 3-10 mL of PRP from each subject. Platelet poor plasma (PPP) can be added to PRP to achieve the desired injection volume. This system is FDA approved by 501k for “clinical laboratory or intraoperatively at the point of care for the safe and rapid preparation of platelet poor plasma and platelet concentrate (platelet rich plasma) from a small sample of whole blood or a small mixture of blood and bone marrow”. For patients randomized to the control arm, they will still have their blood drawn, however it will not be processed to make PRP.

[figure not shown]
9.2 Administration of IP

The patient will be positioned supine. A sterile field will be developed with Betadine prep of the genitalia, sterile gloves and a sterile extremity drape. A total of 20 ml of 1% lidocaine will be drawn up using an 18-gauge needle and will be subcutaneously administered using a 27-gauge needle into the subcutaneous tissue at the base of the penis to obtain a dorsal nerve block. A 1/4-inch Penrose drain will be used as a tourniquet by placing it at the base of the penis and maintaining it in place under tension by a sterile clamp. A maximum of 5mL of PRP will be infused steadily over a two-minute period – approximately 2.5 ml each into the right and left corpus cavernosum. The infusion will be performed at this slow speed (each side over 2 minutes of infusion) to minimize injury to

the platelet cells. In the control arm, men will be administered injectable normal saline that will be injected in a similar manner as the PRP.

Following administration of PRP or normal saline, compression of the penis will be achieved with a clenched fist for 20 minutes. At 20 minutes, the tourniquet will be removed, and a compressive dressing will be placed around the penile shaft. The patient will be instructed to remove the compression bandage in 4 hours and to contact the study coordinators if he experiences any problems.

Figure 1: Diagram of PRP Injection

9.3 Randomization

On Day 0 (V2), participants who remain eligible for the trial will be randomized to one of two groups in a 1:1 ratio. The randomization sequence will be computer generated by the study coordinating team.

9.4 Blinding

The study will remain double-blind by having both blinded and unblinded study teams. All subjects, active-therapy and placebo groups will undergo blood collection procedure on day of intervention visits. Preparation of PRP and normal saline injections will be conducted only by unblinded research team members. In the interest of safety, the study product must be inspected to ensure it is free of air bubbles, clumping, etc.

The 10cc syringes used will be colored and covered in both groups in order to ensure the double-blindness of the study.

If for important medical reasons unblinding of additional team members is thought to be necessary, the Investigator may identify the treatment assignment by obtaining randomization records from unblinded study team.

10. Data Management

Data will be entered from source documents into eCRFs which are maintained in an online research database. The investigator will ensure data integrity by confirming the CRF's are attributable, legible, contemporaneous, original, accurate, and complete.

10.1 Case Report Forms (CRFs)

The Investigator or designee must record all required subject data, and an explanation must be documented for any missing data. This study will use electronic case report forms (eCRF) for data entry and database storage.

10.2 Source Documents

Source data is all information, original records of clinical findings, observations, or other activities in a clinical trial necessary for the reconstruction and evaluation of the trial. Source data are contained in source documents. Examples of these original documents, and data records include: hospital records, clinical and office charts, laboratory notes, memoranda, subjects' diaries or evaluation checklists, recorded data from automated instruments, copies or transcriptions certified after verification as being accurate and complete, and records kept at medical technical departments involved in the clinical trial. All corrections to study data will be made by drawing a single line through the information to be corrected without obscuring it. All corrections will be initialed, dated and explained, if necessary, in accordance with good clinical practice (GCP) guidelines.

10.3 Study Monitoring, Auditing, and Inspecting

The investigator will permit study-related monitoring, audits, and inspections by the IRB, government regulatory bodies, and University compliance and quality assurance groups of all study related documents. The investigator will ensure the capability for inspections of applicable study-related facilities.

11. Data and Specimen Banking

11.1 Storage of Data

Data will be maintained on research team hardware, and subject charts will be stored in a filing room maintained by Department of Urology. Clinical follow up and laboratory data will be stored in a locked room, with access only to authorized personnel. It is up to the principal investigator's discretion as to how long non-FDA study essential documents are retained.

11.2 Specimen Banking

Bio-specimens will be reserved for future testing and stored at -80 degrees Celsius in equipment maintained by ISCI in the Biomedical Research Building (BRB) (address: [name]). Each specimen must have a corresponding requisition form to track the chain of custody from time of collection to time of processing and/or storage.

12. Safety Monitoring and Reporting

12.1 Adverse Events (AEs)

An adverse event (AE) is defined as any untoward medical occurrence associated with the use of a drug in humans, whether or not considered drug related. An AE can be any unfavorable and unintended sign (including an abnormal laboratory finding), symptom, or disease temporally associated with the study. The event does not need to have a causal relationship with treatment. Common Terminology Criteria for Adverse Events Version 5 (CTCAE) will be used for describing AEs. All urological and/or reproductive system AEs will be recorded. For all other AEs, only events greater than grade 2 will be recorded.

We anticipate there to be few adverse events related to the study. Based on the four published studies and abstracts, including 75 men, only minor adverse events were reported (Bruising 1, Mild Pain 4). No serious adverse events were observed [23-26] (Table 2)

| Adverse Events Reported N=75 | |
|------------------------------|---|
| Pain | 4 |
| Bruising | 1 |
| Swelling | 0 |
| Edema | 0 |
| Allergy | 0 |
| Penile | |
| Fracture | 0 |
| New | |
| Penile | |
| Curvature | 0 |

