| STUDY DESIGN | Randomized, Double Blind, Placebo Controlled, Pilot Trial |
| ROUTE OF ADMINISTRATION | Intracavernosal Injection |
| SUBJECT POPULATION | 80 male subjects between the age of 30-75 with erectile dysfunction of organic origin |
| STUDY OBJECTIVES | 
Primary: To investigate and compare the treatment efficacy of PRP vs placebo treatment in men with mild-moderate ED, as measured by IIEF.
 
Secondary: To study incidence of adverse events and safety of PRP injection treatment in men with mild-moderate ED, as measured by IIEF.
 |
| INVESTIGATION PLAN | 
80 men with Erectile Dysfunction (ED) of organic origin, that meet all of the inclusion and none of the exclusion criteria, will be randomized to receive, intracavernosal injection of either PRP or placebo in a 1:1 double-blinded fashion:
 
Group A (40 subjects): Autologous PRP All subjects in this group will receive 2 sessions of autologous PRP with 30 ± 7 day treatment interval. 5mL of PRP will be injected at each session.
 
Group B (40 subjects): Placebo (Normal Saline) All subjects in this group will receive 2 sessions of normal saline with 30 ± 7 day treatment interval. 5mL of normal saline will be injected at each session.
 
 - Patients will be followed for outcome assessments at 1, 3, and 6 months post final injection. |
| DURATION OF STUDY | 9 months (1 month screening, 2 therapy sessions 1 month apart, 6 months follow-up) |
| DEFINITION OF ENDPOINTS | 
Primary Endpoint (Efficacy)
 
 - The percentage of subjects in each group who attain MCID in IIEF-EF domain from baseline to 4 weeks after final treatment. 
Secondary Endpoints (Efficacy)
 
 - The percentage of subjects in each group who attain MCID in IIEF-EF domain from baseline to 12 & 24 weeks after final treatment. - The difference between groups in change of IIEF-EF score from baseline to 4, 12, & 24 weeks after final treatment. - Differences in Doppler ultrasound parameters (PSV and EDV) from baseline to 24 weeks after final treatment. 
Secondary Endpoints (Safety)
 
 - Incidence of adverse events in all patients during the study period. |

| | |
|--------------------|--|

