- The percentage of subjects in each group who attain MCID in IIEF-EF domain from baseline to 12 & 24 weeks after final treatment.
- The difference between groups in change of IIEF-EF score from baseline to 4, 12, & 24 weeks after final treatment.

- Differences in Doppler ultrasound parameters (PSV and EDV) from baseline to 24 weeks after final treatment.

4.3 Secondary Endpoints (safety):

- Incidence of adverse events in all patients during the study period. Anticipated adverse events that will be recorded at every visit are the following
 - o Pain
 - o Bruising
 - o Swelling
 - o Edema
 - o Allergy
 - o Penile Fracture
 - o New Penile Curvature

4.4 Exploratory Endpoints:

- Change in stretched penile length from baseline to 24 weeks after final treatment.
- The percentage of subjects in each group who attain MCID in IIEF-EF domain from baseline to 4 weeks after final treatment.

5. Study Location

The study will be funded by the Department of Urology and coordinated by the University of Miami (UM), Miller School of Medicine, Department of Urology. The UM Interdisciplinary Stem Cell Institute (ISCI) will also support the project (logistics, quality control, management, storage of specimens and data). All study visits will be carried out in the Department of Urology clinics, (ADDRESS: [name], University of Miami Miller School of medicine, Miami, FL. & Lennar address) PRP preparation will take place in the clinic's andrology lab.

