8.2 Description of Study Procedures

8.2.1 *Informed Consent:* Refer to Section 7.3 for details regarding the informed consent process. Study procedures will be completed only after participants have signed the informed consent documentation.

8.2.2 *Demographics:* Demographic characteristics will be recorded including: date of birth, gender, marital status, race and ethnicity. If Medical history has been recorded as part of their participation in another study those source documents may be requested and used for the purpose of this research study.

8.2.3 *Medical History:* Assessment of current and past medical, surgical, and social history will be conducted.

8.2.4 *Physical Examination:* Genitourinary/Reproductive system physical exam will be performed.

8.2.5 *Doppler Ultrasound:* Penile Doppler ultrasound will be performed as standard of care for the management of erectile dysfunction. Results from within the past 12 months can be extracted from the medical record for use in this study.

8.2.6 *Concomitant Medications:* Review of current use of prescription and over the counter (OTC) medications. Participants must discontinue use of PDE5i medications throughout the duration of the study.

8.2.7 *Review Adverse Events:* Refer to Section 12 for description and reporting of adverse and serious adverse events

8.2.8 *Randomization:* Refer to Section 9.3 for details about randomization plan

8.2.9 *Study Therapy Injection:* Approximately 120mL of blood will be collected from participants for preparation of investigational product. Refer to Section 9.2 for description of IP preparation and administration.

8.2.10 *International Index of Erectile Function (IIEF) Questionnaire:* This validated 15-item self-evaluation scale provides pre and post treatment clinic evaluations of erectile function, orgasmic function, sexual desire, satisfaction in sexual intercourse and general satisfaction. If the subject has completed the IIEF questionnaire within the past 6 months, those results may be requested and used for the purpose of this research study. Questionnaires will be completed prior to therapy at injection visits.

8.2.11 *Sexual Encounter Profile (SEP3) Questionnaire:* This 5-item questionnaire is completed after each sexual intercourse attempt. Participants will be asked to complete the short version consisting of question #2 and #3 only.

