12.3 Reporting Responsibilities of the Investigator

Safety monitoring and reporting will be conducted in accordance with all university and departmental standard operating procedures (SOP). The study investigators will report to a surgeon monitor (**[name]**) who is not directly involved in the study, and has been delegated by the sponsor to ensure data quality and subject safety. The investigators will conduct continuous reviews of the safety data, keep track of SAEs and TE-SAEs, which will be discussed at research committee meetings once every 3 months.

Common Terminology Criteria for Adverse Events, Version 5 (CTCAE v5.0) will be used to assess severity of adverse events. All grade 3-5 adverse events, regardless of

association with the IP, will be entered into study database and reviewed at research committee meetings. In addition, all SAEs will be entered into research database and reviewed by the surgeon monitor on an ongoing basis. If a death occurs within 30 days of investigational therapy, and is determined to be related to the study, the investigators will notify the Urology Department Chair (**[name]**) within 1 business day. If an increase in the frequency of grade 3 or 4 adverse events is noted in the study, a report will be submitted to the Department Chair at the time the increased rate is identified. If at any time the principal investigator stops enrollment or stops the study due to safety issues, the Department Chair will be notified within 1 business day and a formal letter will be sent to the Department Chair to be received within 10 business days.

13. Statistical Considerations

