13.2 Sample Size

Inclusion Criteria are men with IIEF scores >11 which includes men with mild (IIEF 16-21) and mild/moderate (12-16) Erectile dysfunction. Minimal clinically important differences (MCID) for these groups are an increase of 2 for mild and 5 for moderate ED. Previous studies on the effect of placebo show about a 15% improvement in men with mild to moderate ED. Therefore, 15% of the placebo group is expected to meet MCID. Results from the PRP safety study by Matz et al. 2018, which showed a mean improvement in IIEF of 4.14 points in seven patients with ED after PRP. In the interventional group, we expect 50% to meet MCID. At 80% power, we will therefore need 30 patients in each group to detect a difference of 35% between treatment and placebo arms.

$$\text{Sample size} = \frac{2(Z_{\alpha/2} + Z_{\beta})^2 P(1 - P)}{(p_1 - p_2)^2}$$

$$28.08 = (2*(1.96+0.84)^2 * (0.25*(1-0.25)) / (0.35^2)$$

Assuming attrition of approximately 20%, an additional 6 participant slots will be added to each group for a total sample size of 80 subjects.

14. Risks to Subjects

We anticipate there to be few adverse events related to the study. Based on the four published studies and abstracts, including 75 men, only minor adverse events were reported (Bruising 1, Mild Pain 4). No serious adverse events were observed [23-26] (Table 2). After literature review, we believe this product to be of non-significant risk to patients (NSR) and for investigational use in a clinical study protocol.

Based on published studies, we will record anticipated adverse events to patients include: local injection site reaction, penile pain and penile bruising. Additionally, we anticipate

patients may experience, penile swelling, allergic reaction, local infection (though none reported in previous studies) and will record them at every visit systematically.

15. Potential Benefits to Subjects

The potential benefits for men randomized to the treatment arm will include improvement in erectile function and sexual performance.

16. Privacy & Confidentiality

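### The rule in Section 12.1 to record non-urological adverse events only above grade 2 cannot deliver the safety endpoint, which sets no grade or body-system limit

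*Combined protocol and SAP*

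**What the plan says.** The synopsis and Section 4.3 define the safety endpoint in the same words: "Incidence of adverse events in all patients during the study period". Neither limits it by grade, body system or relation to treatment. Section 4.3 then lists events to be recorded at every visit: pain, bruising, swelling, edema, allergy, penile fracture and new penile curvature. Section 14 gives an overlapping list. It names injection-site reaction, penile pain and bruising, and goes on to say that "patients may experience, penile swelling, allergic reaction, local infection (though none reported in previous studies) and will record them at every visit systematically". It sets no grade limit either.

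Section 12.1 starts from a broad definition that needs no causal link to treatment: "An adverse event (AE) is defined as any untoward medical occurrence associated with the use of a drug in humans, whether or not considered drug" […]. It then gives two recording rules. The first is "All urological and/or reproductive system AEs will be recorded". The second is "For all other AEs, only events greater than grade 2 will be recorded". Severity is graded by CTCAE version 5, so the second rule means grade 3 or higher.

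Section 12.3 uses the same cut-off for database entry and committee review ("All grade 3-5 adverse events, regardless of" association with the product), and adds all SAEs. The schedule of events has adverse events reviewed at V2 to V6.

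**The concern.** The endpoint counts events that staff are told not to write down. No section narrows the endpoint to fit Section 12.1, and none says whether the lists in Sections 4.3 and 14 override the grade threshold.

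Both arms undergo procedures that can cause mild systemic effects. Section 8.2.9 says: "Approximately 120mL of blood will be collected from participants for preparation of investigational product". Sections 9.1 and 9.4 apply the blood draw to the control arm as well, on the day of each injection visit. Section 9.2 adds a lidocaine nerve block. A low-grade systemic effect of PRP itself would also fall under the second rule unless it were allergy.

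The synopsis labels the study Phase I, safety is the stated secondary objective, and Section 2.2 says that no randomized placebo-controlled studies exist. Section 12.2 anticipates no SAEs related to study procedures. For non-urological events, the rule therefore removes the grades at which events are most to be expected. An overall incidence reported from these data would promise more than was collected.

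**Working it through.** The documents state no figure for this point, so there is nothing to reproduce. The check compares the recording rules by type of event, under the two possible readings.

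| Event | If 12.1 governs | If the lists in 4.3 and 14 override 12.1 |
|---|---|---|
| Urological or reproductive, any grade | recorded | recorded |
| Non-urological, grade 3 or higher | recorded | recorded |
| Any SAE | entered under 12.3 | entered under 12.3 |
| Allergy not classed as urological, grade 1-2 | not recorded | recorded |
| Other non-urological, unlisted, grade 1-2 | not recorded | not recorded |

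The endpoint as worded includes all five rows. The last row is lost on either reading. The allergy row depends on which text prevails, and the documents do not say.

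**Illustration of size.** The documents give no rate for such events, so these figures show a range and are not estimates.

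Inputs:
- n = 80 men, 40 per arm (synopsis).
- p = assumed share of men with an unlisted non-urological event.
- g = assumed share of those men whose event is grade 3 or higher, and so recorded.

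Men whose event is missed = n × p × (1 − g):
- p = 5%: 80 × 0.05 = 4 if g = 0; 4 × 0.8 = 3.2 if g = 20%.
- p = 10%: 80 × 0.10 = 8; 8 × 0.8 = 6.4.
- p = 20%: 80 × 0.20 = 16; 16 × 0.8 = 12.8.

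Chance of at least one such man among the 40 given PRP, with g = 0, is 1 − (1 − p)^40:
- p = 5%: 1 − 0.95^40 = 0.871.
- p = 10%: 1 − 0.90^40 = 0.985.
- p = 20%: 1 − 0.80^40 = 0.9999.

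**Check against the only prior data in the protocol.** The four cited studies give 9 + 16 + 10 + 40 = 75 men and 4 + 1 = 5 events, as Section 12.1 states. All five were pain or bruising, so no event of another type was reported. The exact one-sided 95% upper bound for 0 of 75 is 1 − 0.05^(1/75) = 3.9%, which is below the lowest rate assumed above. At that bound, 80 × 0.039 = 3.1 men would be affected.

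**The case against.** The strongest reply is that the threshold is an open design choice for a local penile injection, and that the plan keeps what matters most. Much of this stands.

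- Urological and reproductive events are recorded at every grade, the listed local events are recorded at every visit, and pain is also scored by VAS after each injection. All five events in the earlier studies were of listed types. A reader might infer that nearly all low-grade safety information is lost; the documents do not support that.
- A reader might infer that mild allergic reactions will go uncounted. On an ordinary reading, a list that names allergy is not displaced by a residual rule for other events. Allergy is probably captured, though no section says so.
- A reader might infer that reactions to the nerve block are excluded outright. The block is given at the base of the penis, so local reactions there are plausibly genital events, and most are listed anyway. Only unlisted low-grade systemic effects fall out.
- A reader might infer that the rule favours PRP. It is the same in both arms, and both arms have the blood draw and the block, so it does not by itself bias the comparison.
- The 5% to 20% rates are assumptions, and the earlier studies point lower. That evidence is weak, because the documents do not show how those studies collected adverse events.

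None of this rescues the last row of the comparison. An unexpected systemic effect is, by its nature, not on a list of anticipated events.

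**Conclusion.** The point holds in a limited form. If Section 12.1 is followed, unlisted grade 1-2 non-urological events are never recorded, whichever reading of the lists is taken. Any such event makes the endpoint as worded an under-count, and a low-grade systemic difference between arms cannot be seen. Loss of allergy events is possible, not certain.

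The size of the under-count is unknown. The range of 4 to 16 of 80 men assumes rates of 5% to 20% with none at grade 3 or higher; the true number could be smaller. The conclusion rests on the text and not on those rates. The efficacy comparison is untouched. The plan should be corrected because the omission limits what the trial can say about safety, and events that were not written down may not be recoverable later.

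**What to change.** Amend Section 12.1 so that adverse events of any CTCAE grade and any body system are recorded in both arms at the reviews already scheduled for V2 to V6. Align Section 12.3 so that these events are entered in the database, while the grade 3-5 cut-off may stay as the trigger for committee review. Report incidence by arm, grade and body system. The cost is a short amendment and modest extra data entry for 80 men; no visit is added.

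If the sponsor prefers to keep the threshold, the least that is needed is two statements. First, all events listed in Sections 4.3 and 14 are recorded at any grade, which settles allergy, local infection and injection-site reaction. Second, the endpoint in the synopsis and Section 4.3 is urological, reproductive and listed adverse events of any grade, plus other adverse events of grade 3 or higher. This costs only wording and avoids claiming an overall incidence from truncated data, but low-grade systemic events would still go unseen.
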